Subjects were excluded if they had transposed, impacted, or missing teeth, previous history of orthodontic or orthognathic surgical treatments, treatments that involved tooth extractions or orthognathic surgery, systemic illness or craniofacial syndrome or disorder, missing appointments, and compromised oral hygiene. Subjects who had radiographic bone loss observed on the dental panoramic image were excluded. Additionally, any drugs that affect tooth movement used prior to the beginning of, or during the study would also exclude the subject.

Sample size

Sample size was calculated based on the results of Scott et al.³⁴ that determined a standardized difference of 0.98 in the rate of tooth alignment within a period of 34 days would give a clinically relevant difference of 0.8 mm between two groups. For statistical power of 80% at a significance level of 0.05, 17 subjects were needed in each group for a total sample size of 34 subjects.

Study time points

Total observation duration for all study participants was 18 weeks from the first day of bonding maxillary and mandibular arches, which were both bonded on the same appointment.

Periodic records included intra-oral photos and an intra-oral scan for all subjects at the records appointment (T1), at 6 weeks – first adjustment visit (T2), at 12 weeks second adjustment (T3) and at 18 weeks third adjustment (T4). During each visit, in addition to the periodic records including intra-oral photos and scans, any broken brackets were repositioned for both groups.

Outcome Measures

There were two outcomes measured in this study, the effectiveness of tooth movement and patient comfort at 6, 12 and 18 weeks after appliance bonding.

A] Effectiveness of tooth movement:

1. Alleviation of crowding: Little's Irregularity Index (LII) which measures the alignment discrepancy in the five contact points of the lower anterior region was assessed between T1 and T4 for every patient. The scores were measured digitally by identifying the center of the mesial (CoM) and distal (CoD) contact points on each tooth at the same vertical level. The 3D slicer software was used to measure the horizontal distance between CoM and CoD of adjacent teeth in millimeters. The scores were then compared between the two groups (BR and LFFA) and comparisons were made in the different timepoints within each group.

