2. Changes in 3D individual tooth positions: To assess the extent of movements achieved in all three planes for each maxillary and mandibular tooth from 6-6, digital model superimpositions were performed using 3D Slicer software (www.slicer.org Harvard University, Boston, MA, USA). Maxillary superimpositions were done based on the method described by Aliaga et al.³⁵ using the palatal rugae. Mandibular superimposition was completed by overlaying the pre- and post-treatment digital models on the mucogingival junction which is a stable and reliable landmark according to a study by Ioshida et al.

B] Patient comfort level

Data obtained from the perceived comfort questionnaires was evaluated by identifying chronological pattern of any pain experienced as well as any other patterns according to the data obtained. The extent of comfort will be described by a percent at each time point, two-sample independent t-test will be done to compare the pain between the two groups.

Comfort level was assessed using an electronic survey instrument developed by Wu et al.³⁷ (Appendix 2). This valid and reliable instrument used a VAS score to assess the overall comfort, comfort in the tongue, cheeks, lips, gingiva, and face and jaw.³⁸ It also asked about the use of medications. The survey instrument was sent online to patients through QuestionPro (Austin, TX, USA). Each patient was instructed to complete and submit the survey daily, on the first seven days after their first visit (T1), second visit (T2), third visit (T3) and fourth visit (T4).

Procedure of the study

Subject Randomization

Prior to initiating sample recruitment, block randomization was carried out by a statistician who was not involved in recruiting or treating patients. Results of the randomization, whether BR or LFFA were written down on 34 different sheets of paper. Each sheet was then individually enclosed in opaque sequentially numbered envelopes. An envelope corresponding to the number of the sample joining the study would be opened to find out which group the new sample would fall into.

Subject recruitment process

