All tooth movement data were assessed for normality with the Shapiro-Wilks test. Sample sizes were relatively small in both the BR and FFA groups, so the power of this test to correctly identify non-normal distributions is likely low. Therefore, t-tests for differences between groups were performed where appropriate along with the Mann-Whitney nonparametric tests. The difference in between group continuous questionnaire outcomes and continuous demographic data were also evaluated for significance with the Mann-Whitney test. The within group tests for the paired differences in T1 and T4 values of Little's Irregularity Index were done with the Wilcoxon signed rank test. Categorical questionnaire outcome and categorical demographics data associations with the BR and FFA groups were tested for independence using Fisher's exact test, since there were instances of low (< 5) or and zero cell counts. A post hoc power to sample size analysis using Little's Irregularity Index data was also performed under an assumption of normality. The estimated effect size used was determined by first calculating the mean of the paired T1 to T4 differences in both the BR and FFA groups, and then taking the difference between these group means. The standard deviation for the sample size calculations was taken as the pooled value of the standard deviations of both groups' paired differences. All statistical analysis was performed using R (v4.0.4) through RStudio (v.461).

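### Medication use and other categorical survey answers are collected on up to 28 days per patient, but the Fisher's exact test named for them has no stated unit of analysis; a per-patient count of days would use the data better

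*Combined protocol and SAP*

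**What the plan says.** Outcome Measures, B] Patient comfort level, sets the survey schedule: "Each patient was instructed to complete and submit the survey daily, on the first seven days after their first visit (T1), second visit (T2"), then "third visit (T3) and fourth visit (T4"). Of the instrument it adds: "It also asked about the use of medications". On reporting, it says: "The extent of comfort will be described by a percent at each time point". It does not define whether a time point is a day or a visit week.

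The Statistical Analysis section gives one method for the categorical items: "Categorical questionnaire outcome and categorical demographics data associations with the BR and FFA groups were tested for independence using Fisher's exact test". The reason given is "since there were instances of low (< 5) or and zero cell counts". The section names no day, visit, per-patient summary, adjustment for repeated answers or limit on the number of tests. For continuous questionnaire outcomes it uses the Mann-Whitney test.

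**The concern.** Fisher's exact test assumes one independent answer per patient. Sparse cells are a reason to prefer it to a chi-squared test, but they do not deal with repeated answers from the same person. Because the unit is unstated, a reader cannot tell what a reported p-value means. A null result could come from a table that used one day in 28. An isolated positive could be one of many daily tests.

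The point covers only categorical items asked daily, with medication use as the named example. It does not concern the VAS scores or the demographics. Comfort is one of the trial's two outcomes, but medication is only one item within it.

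**Working it through.** **Inputs from the documents**
- Scheduled surveys per patient: 7 days × 4 visits = 28 (Patient comfort level).
- Patients: 17 per group (Sample size). One week gives 17 × 7 = 119 answers per arm, and four weeks give 17 × 28 = 476.
- Test level: "at a significance level of 0.05" (Sample size), taken as two-sided because the side is not stated.

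**Assumed, because the documents give no figure**
- A yes/no answer with a constant daily rate: 30% in both arms for false positives, 20% v 50% for power.
- Within-patient correlation (ICC) of 0.2 to 0.6, simulated with a beta-binomial model.

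**1. The plan's own figure.** n = 2(1.960 + 0.842)² / 0.98² = 16.3, rounded up to 17 per group. This reproduces the stated size. It was set for tooth alignment, so its 80% power does not carry over to the survey items.

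**2. One answer per patient.** Enumerating all 18 × 18 possible tables for 17 v 17, Fisher's true size never exceeds 2.4%, and it is 2.0% at a 30% rate. The test is valid but conservative. Its power for 20% v 50% on one preselected day is 32%.

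**3. A table for every day.** With no true difference, the chance of at least one significant daily test is about 10-13% over 7 days and 21-39% over 28.

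**4. Pooled days, if they were used.** The design effect is DE = 1 + (m − 1) × ICC, and the approximate false-positive rate is 2[1 − Φ(1.96/√DE)].

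| ICC | m = 7: DE, rate | m = 28: DE, rate |
|---|---|---|
| 0.2 | 2.2, 19% | 6.4, 44% |
| 0.6 | 4.6, 36% | 17.2, 64% |

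Simulating Fisher's test itself gives about 15-34% for 7 days and 42-63% for 28.

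**5. Power over one survey week, 20% v 50% of days**

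| Analysis | Power |
|---|---|
| Fisher, one day | about 30% (32% exact) |
| Fisher, ever used in the week | 46-52% |
| Mann-Whitney, days of use per patient | 64-91% |

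The Mann-Whitney test on days keeps its size, at 4.2-5.3%.

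**6. If use falls after a visit.** With assumed daily rates of 20/10/5/2/1/1/1% v 60/30/10/2/1/1/1%, power is about 54% for Fisher on day 1, 51-54% for ever-used Fisher and 62-67% for Mann-Whitney on days. The gain is then roughly 10 points.

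**The case against.** The strongest reply is that Fisher's test is not wrong here. Applied to one ever-used answer per patient it is valid. In the scenario of step 5 it keeps more than half of the power of the count, and in some scenarios it costs nothing: for 10% v 30% over 28 days at ICC 0.5, ever-used Fisher and a per-patient t-test both reach 54%. That stands, so the plan's test cannot be said in general to lose most of the power. The opposite extreme also occurs: when almost everyone takes medication at least once, an ever-used table has almost no power (0% against 99.8% for 30% v 60% over 28 days at ICC 0.1).

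A reader might infer that days were pooled and that false positives are therefore inflated several-fold. No section says so. The mention of low and zero cell counts points away from it: at a 20% rate, pooling would give about 0.2 × 119 = 24 positive answers per arm in one week and 0.2 × 476 = 95 in four. This is not proof, because the same sentence also covers demographics.

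A reader might also infer that daily tables would usually miss a real difference. Under the 20% v 50% model, at least one daily test is significant in 68-85% of trials over 7 days and in 81-99% over 28. The main risk of daily tables is uncontrolled false positives.

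Two further points stand. Constant daily rates favour the count, as step 6 shows. And the section on comfort seeks a chronological pattern, which a count alone would lose.

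**Conclusion.** The concern holds in this limited form. Up to 28 answers per patient are tested by a method that needs one, and the plan does not say how the answers are reduced. This is more than a missing detail, because a better analysis of the same data is available with a test already in the plan. Under constant rates of 20% v 50% and ICC 0.2 to 0.6, the count reaches 64-91% power over one week, against 46-52% for the best valid Fisher table. Under a steep fall after each visit the advantage is roughly 10 points. All these sizes rest on assumed rates and correlation.

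The false-positive figures for pooled days are conditional and are not a finding about what was done. The documents also do not support treating medication use as the key comfort measure, since comfort is scored mainly by VAS. Nor do they make Fisher's conservatism an error that calls for a different exact test.

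**What to change.** 1. For each patient and survey week, compute days with medication out of days answered. Compare arms with the Mann-Whitney test already in the Statistical Analysis section, and report the difference in mean days with a 95% confidence interval.
2. Name one comparison as the main one, for example the share of days over all four weeks, or adjust across weeks. Four unadjusted weekly tests would carry up to 1 − 0.95⁴ = 18.5% if they were independent.
3. Do not pool days into one table. Show day-by-day percentages by arm descriptively to keep the time pattern. If the daily course is to be tested, use a GEE or logistic mixed model clustered on patient, with a small-sample correction because there are only 34 patients.
4. Keep Fisher's test for demographics and other items answered once per patient. For any Fisher test already run on survey items, state the day, visit or summary used and how many tests were run.

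The cost is a few sentences of SAP text and a few lines of R, with no new data. Because the section is written in the past tense, a re-analysis should be labelled as post hoc. The count does not show on which day medication was taken, and unanswered days must be handled through the denominator, so days answered should be reported by arm.

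### The post hoc sample size analysis uses the trial's own observed group difference as its effect size, and no confidence interval for that difference is specified

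*Combined protocol and SAP*

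**What the plan says.** The Statistical Analysis section announces "A post hoc power to sample size analysis" on Little's Irregularity Index, assuming normality. Its effect size comes from the trial: "The estimated effect size used was determined by first calculating the mean of the paired T1 to T4 differences" in both groups, "and then taking the difference between these group means". So does its variability: "The standard deviation for the sample size calculations was taken as the pooled value of the standard deviations" of the two groups' paired differences. No purpose and no numerical result are given.

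Between-group results are described only as tests. For tooth movement, "t-tests for differences between groups were performed where appropriate along with the Mann-Whitney nonparametric tests"; the questionnaire and demographic data get Mann-Whitney or Fisher's exact tests. No confidence interval is specified for any estimate. The same section concedes that "Sample sizes were relatively small in both the BR and FFA groups".

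The Sample size section rests on a different quantity. It cites an earlier study for its planning effect: "standardized difference of 0.98 in the rate of tooth alignment within a period of 34 days would give a clinically relevant difference of 0.8 mm". From this it arrives at 17 per group for 80% power at the 0.05 level. Study Design calls the trial a pilot and sets the alignment comparison at T1 against T4, 18 weeks after bonding.

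**The concern.** An effect size estimated from about 17 patients per group carries a large sampling error. Fed into a sample size formula, where it enters as an inverse square, that error is magnified. A later trial planned this way could by chance alone be several times too small or too large. If the analysis is meant as observed power, it adds nothing to the p-value of the matching t-test.

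What a reader of a small pilot needs is the range of 18-week differences compatible with the data. A confidence interval gives that, and the plan does not commit to one. The planned 80% power does not fill the gap: it is for an alignment rate over 34 days, and the documents give neither an SD nor a relevant difference for the 18-week change.

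**Working it through.** All calculations are two-sided at 0.05 with equal groups.

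**Inputs from the documents.** d = 0.98, 0.8 mm, 34 days, 80% power, alpha 0.05 and 17 per group (Sample size); T4 at 18 weeks (Study Design). The analysed group sizes, the observed difference and its SD are not given. The true d values of 0.5 and 0.8, the SDs other than 0.816 mm, and 14 per group (to show some loss) are assumptions.

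**1. The plan's own figure.** Normal approximation: n = 2(1.960 + 0.842)²/0.98² = 16.35, rounded up to 17. This reproduces. Power at 17 per group is 81.5% by the normal approximation and 79.1% by the noncentral t.

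**2. Different time and scale.** 18 × 7 = 126 days, against 34. The T2 scan at 6 × 7 = 42 days is close to 34, but the index comparison is T1 to T4.

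**3. The post hoc result as a function of p.** With observed difference and pooled SD, t = d√(n/2), so d = t(1 − p/2; 32 df) × √(2/17).

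| p | observed d | power at that d, 17 per group | n per arm for 80% |
|---|---|---|---|
| 0.05 | 0.699 | 51% | 34 |
| 0.20 | 0.449 | 25% | 79 |
| 0.50 | 0.234 | 10% | 288 |

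Here p belongs to an equal-variance t-test on the T1 to T4 changes. The plan does not say that this was the reported test for the index (Outcome Measures speaks of comparing scores), so this is a property of the calculation. It does not show that a reported p-value was repeated.

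**4. Spread when sizing from the observed effect.** The observed d has the distribution of √(2/17) × noncentral t(32 df, noncentrality d√(17/2)); its absolute value gives n for 80% power. The comparator keeps the difference at its true value and takes only the pooled SD from the pilot, with s/σ = √(χ²(32)/32), whose 10th and 90th percentiles are 0.834 and 1.154.

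| True d | n per arm needed | From observed effect, 10th–90th percentile | Chance later trial has under 50% true power | Difference fixed, pilot SD only | Same chance |
|---|---|---|---|---|---|
| 0.5 | 64 | 18 to 1048 | 27% | 45 to 85 | 0.6% |
| 0.8 | 26 | 11 to 122 | 18% | 19 to 34 | 0.7% |
| 0.98 | 18 | 9 to 56 | 14% | 13 to 23 | 0.6% |

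With 14 per group the observed-effect ranges at d = 0.5 and 0.8 are 16 to 1221 and 10 to 156, with chances of 29% and 21%.

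**5. Precision of the group difference.** The 95% CI half-width is t(0.975; 2n − 2) × √(2/n), in SD units: 0.70 at 17 per group and 0.78 at 14. The difference detectable with 80% power is 0.99 SD at 17 and 1.10 SD at 14.

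**6. Power for 0.8 mm at T4.** The SD of the 18-week change is unknown. The Sample size figures imply 0.8/0.98 = 0.816 mm, but for the 34-day quantity.

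| SD (mm) | 17 per group | 14 per group |
|---|---|---|
| 0.6 | 96% | 92% |
| 0.816 | 79% | 70% |
| 1.0 | 62% | 53% |
| 1.5 | 33% | 27% |
| 2.0 | 20% | 17% |

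Power for a given millimetre difference at 18 weeks may therefore lie above or below 80%.

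**The case against.** The strongest reply is that the harm depends on an inferred purpose. No section mentions a later trial, and the calculation sets no test, threshold or enrolment number here. That is correct, and it keeps the point minor. It does not remove it: as planning input the calculation is unstable, as observed power it is redundant, and the remedy is the same on either reading.

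A second reply is that pilots routinely supply planning inputs. This stands for the SD, which is not criticised. The comparison in step 4 shows that the instability comes almost entirely from the observed effect.

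A third is that the assumed effects of 0.5 and 0.8 lie below the only standardized difference in the documents, and that the upper extreme of 1048 arises at an observed d of about 0.12, on which few would plan a trial. This is fair as to the extremes. At 0.98 the range is much narrower, but 9 to 56 per arm against 18 needed, with a 14% chance of under 50% power, is still a poor basis.

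Finally, the plan does not rule out a confidence interval, and the group means and pooled SD it already computes would yield one. True, but it does not commit to reporting one. The 34-day against 18-week mismatch is a separate weakness of the Sample size section. It matters here only because it means that the planned power cannot stand in for an interval.

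**Conclusion.** The concern holds, as a minor point. The effect size and SD of the post hoc analysis both come from the trial's own data, and no confidence interval is specified. With 17 per group, a sample size derived from the observed effect ranges over roughly 6-fold (9 to 56 per arm at a true d of 0.98) to 58-fold (18 to 1048 at 0.5) between the 10th and 90th percentiles. With a fixed difference and the pilot SD the range is under 2-fold. The chance of a later trial with under 50% true power is 14% to 27%, against under 1%.

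These ranges rest on normality, equal variances, 17 analysed per group and the true d values shown. The half-width of 0.70 SD and the dependence on p need no assumed effect. That the analysis is meant to size later work is an inference from the pilot label.

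**What to change.** **Statistical Analysis.** Drop the power calculation based on the observed effect. Report the between-group difference in T1 to T4 change in the index with its 95% CI and the number analysed per group. If a sample size for a later trial is given, combine the pooled SD already computed with an 18-week difference justified independently of the observed one, and show the result over a range of differences and SDs. The 34-day 0.8 mm should not be carried over by default.

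**Sample size.** State that the 80% (79% by t-test) refers to the 34-day effect and is not claimed for a millimetre difference in T1 to T4 change. Give the detectable difference for that change as about 0.99 SD if all 17 per group are analysed, and larger if fewer are (1.10 SD at an assumed 14).

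**Cost.** One calculation is replaced by an interval from data already collected, plus a sentence or two. No patients, measurements, endpoints or tests change. The power statement becomes less favourable, and a later-trial sample size will need an 18-week relevant difference that the plan does not yet have.
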